3.2.2 Risk/benefit and ethical assessment

D961H is a proton pump inhibitor (PPI) and is the S-enantiomer of racemate omeprazole.

Omeprazole was approved in Japan on 18 January 1991 for the indication for gastric ulcer, duodenal ulcer, anastomotic ulcer, reflux esophagitis, and Zollinger-Ellison syndrome at a dose of 10 to 20 mg given once daily. Since its commercialisation, omeprazole has been widely used in the clinical practice and the efficacy and safety of the drug have been well established.

The planned indication of D961H is prevention of NSAID-associated peptic ulcers, and long term combination therapy with D961H and NSAID will be assumed; therefore, it is necessary to review the safety of long-term combination therapy with D961H and NSAID. In the overseas clinical studies (I-1001, I-1002, I-1003, and I-1004), the preventive effects of omeprazole against NSAID-associated peptic ulcers were examined. The incidence of AEs in the omeprazole group (60.1-67.6%) was similar to that for the ranitidine group (58.3%) and MISO group (71.4%) and it seemed slightly higher than that for the placebo group (53.2%). The reason why the incidence of AEs in the omeprazole group was slightly higher comparing with the placebo group was considered that there were a number of subjects who discontinued the study treatment due to development of gastric and/or duodenal ulcers and this may have been the influence to shorten the treatment period for the group. Most common AEs observed in each study in which the treatment with omeprazole and its preventive effects were examined as mentioned above were gastrointestinal related events (diarrhoea, abdominal pain, meteorism, etc.) in all treatment groups including the placebo group. As for the incidence of SAEs, there was no remarkable difference between the omeprazole group and control groups (including the placebo group) in all clinical studies mentioned above. Based on these results, it was considered that a trend of the incidence of AEs in the combination therapy with omeprazole and NSAID would not markedly differ from that was seen in the monotherapy group given NSAID alone (i.e., placebo group) or in the combination therapy group given NSAID and ranitidine or MISO. For this, there is little possibility that unexpected or new safety problem is caused by the concomitant therapy with omeprazole and NSAID.

As for the possibility of the drug interactions when omeprazole is used concomitantly with NSAID, clinically significant drug interactions occur at the low possibility ([Andersson T, et al., 1998](#)) based on the results of the overseas clinical studies of NSAID (naproxen, diclofenac, and piroxicam) and omeprazole in combination therapy to investigate pharmacokinetic drug interactions (SH-OMN-0002, SH-OMN-0003, and SH-OMN-0004).

Meanwhile, D961H is not approved in Japan but it has been approved in more than 95 overseas countries, mainly for the treatment of gastroesophageal reflux disease. The evaluation of the postmarketing surveillance data, after more than 397 million delivered treatment courses (as of 10 August 2006), has not revealed any unexpected safety issues.

In Japan, the tolerability of repeated administration of placebo (18 subjects), D961H 10 mg (24), 20 mg (24) and 40 mg (24) once daily for 5 days was examined in 90 healthy male Japanese subjects (SH-QBE-0098). Two AEs (pharyngeal discomfort and epigastric discomfort) were observed in 40 mg group, and one AE (a common cold) was observed in 20 mg group. As all three AEs were of mild intensity and assessed as not related to D961H, it was judged that there is no safety concern about conducting the study.

In the overseas studies (SH-NEN-0002, SH-NEN-0004, SH-NEN-0013, SH-NEN-0014), the long-term safety of D961H used concomitantly with NSAID was examined. The frequency of patients reporting AEs was about 64% in all treatment groups (D961H 20 mg, D961H 40 mg, placebo). The most common AEs during treatment with D961H for 6 months were gastritis and flatulence. Symptoms from the gastrointestinal disorders were the most commonly reported system organ class of AEs. For this, there would be little possibility that unexpected or new safety issues are caused by the concomitant therapy with D961H and NSAID, as in the case of omeprazole.

The general rule used to predict the possibility of metabolic drug-drug interactions between compounds is that interactions are most likely to be limited to drugs metabolized by the same enzyme. Since D961H is mainly metabolised by cytochrome P450 (CYP) isoform, CYP2C19 and CYP3A4 ([Andersson T, et al., 1990](#), [Andersson T, et al., 1993](#), [Chiba K, et al., 1993](#), [Andersson T, et al., 1994](#)), and the NSAID has been shown to be mainly metabolized by another CYP isoform, CYP2C9 ([Leemann T, et al., 1993](#), [Newlands AJ, et al., 1992](#), [Leemann TD, et al., 1993](#)). A drug-drug interaction at the metabolism level would not be expected to appear during coadministration of D961H and NSAID. The clinically significant drug interactions may occur at low possibilities when D961H is used concomitantly with NSAID based on the results from the overseas clinical studies of NSAID (naproxen and rofecoxib) and D961H in combination therapy to investigate pharmacokinetic drug interactions (SH-NEN-0016 and SH-NEN-0017).

3.3 Selection of study population

3.3.1 Study selection record

The investigator(s) must keep a record of subjects who were considered for enrolment but were never enrolled. This information is necessary to establish that the subject population was selected without bias.

3.3.2 Inclusion criteria

For inclusion in the study subjects must fulfil all of the following criteria:

1. Provision of written informed consent (including written informed consent to a genetic test)
2. Medical history of gastric and/or duodenal ulcer. This is defined as the presence of a gastric or duodenal ulcer scar confirmed by EGD findings obtained within two weeks prior to the registration. The test data obtained before informed consent can be used with the consent of the subjects, if the test was conducted within two weeks prior to the registration. In the case that the results of the test did not demonstrate the scar clearly but the subject had an evidence of ulcer conformed by EGD performed in the past he/she will be eligible.
3. A diagnosis of a chronic condition (rheumatoid arthritis, osteoarthritis, lumbago, etc.) that is expected to require daily NSAID treatment during the study treatment period. Daily NSAID treatment is defined as taking the prescribed dose at least 5 out of 7 days each week following the physician's instruction.
4. Dose* and type of the NSAID must be:
 - expected to be used at a constant dose during the period from the registration to the day of the last scheduled visit.
 - administered orally. Additional oral NSAID and external application with NSAID are acceptable in addition to daily oral NSAID.

* Handling of aspirin when used as a analgesic agent:

- 1) When aspirin alone is used, the dose should be more than or equal to 1000 mg/day.
 - 2) When aspirin is used as an additional NSAID, the dose should be more than 324 mg/day.
5. Following criteria must be satisfied when Disease-Modifying Antirheumatic Drug (DMARD [such as methotrexate]) is taken:
 - If the subject has been taking DMARD before registration, it must have been taken for four weeks or longer before registration at the constant dose.
 - DMARD is expected to be taken at the constant dose during the period from the registration to the day of the last scheduled visit.

Rationale for inclusion criteria

1. Established as the part of ethics requirements in accordance with 'Good Clinical Practice (GCP).
2. In order to enrol patients at a high risk to develop NSAID-associated peptic ulcer, a history of gastric and/or duodenal ulcers is included in the criteria as a risk factor.
3. In order to enrol patients at high risk to develop NSAID-associated peptic ulcer, this criterion is established to assure that patients who require the long-term treatment with NSAID are enrolled.

4. This criterion is established since there is a relationship between the doses of NSAID and development of peptic ulcer (Rodriguez G, et al., 1994, Singh G, et al., 1998, Carson JL, et al., 1987, and Griffin MR, et al., 1991). Thus, influences of NSAID on the evaluation of the efficacy of D961H will be minimised by providing the conditions for use of NSAID.
5. This criterion is established to minimise the influence of DMARD on the evaluation of the efficacy of D961H by defining the requirement when DMARD are taken.

3.3.3 Exclusion criteria

Any of the following is regarded as a criterion for exclusion from the study:

1. Less than 20 years of age at the time of informed consent obtained.
2. Having gastric or duodenal ulcer in active or healing stage according to the Sakita/Miwa classification.
3. History of esophageal, gastric or duodenal surgery, except for simple closure of a perforation.
4. Having severe liver disease, including cirrhosis and acute or chronic hepatitis.
5. Liver enzyme (AST, ALT, or ALP) or the total bilirubin level three times the upper limit of reference values at laboratory tests conducted within 2 weeks prior to registration.
6. Having a chronic renal disease or impaired renal function or serum creatinine >2.0 mg/dL as a result of laboratory test conducted within 2 weeks prior to registration.
7. Current or historical evidence of the following diseases/conditions:
 - Zollinger-Ellison syndrome
 - Inflammatory bowel disease (IBD)
 - EGD evidence or suspicion of a (non NSAID-related) pathologic or infiltrative process in gastric and/or duodenum (e.g., Crohn's disease, malignancy, sarcoidosis, amyloidosis, ischemic disease)
 - Any condition that requires surgery during the study period (from the day of informed consent to the day of the last scheduled visit or withdrawal).
8. History of malignant disease except for mild superficial cutaneous disease (within 5 years before registration)
9. Current or historical evidence (within 12 weeks prior to registration) of the following diseases/conditions:
 - Malabsorption
 - Esophageal stricture
 - Esophagitis, other than simple erythema

- Endoscopic Barrett’s esophagus (columnar-lined epithelium more than or equal to 3 cm) or dysplastic changes (based on the documented findings) of any grade in the esophagus
 - Signs and symptoms of gastric outlet obstruction (e.g., abdominal distension or multiple episodes of vomiting)
 - Pancreatitis
 - Severe cardiovascular or pulmonary disease
 - Diabetes mellitus uncontrolled on dietary management, exercise therapy or medication
 - Cerebral vascular disease, such as cerebral ischemia, infarction or haemorrhage.
10. Pregnancy or lactation. Women of childbearing potential must have a negative urine pregnancy test at screening, and have to maintain effective contraception during the study period as judged by the investigator(s).
11. Use of any other investigational product or participation in any other clinical study within 4 weeks prior to registration.
12. Prior enrolment in the study. (Only of subjects who are confirmed having gastric or duodenal ulcer in active or healing stage according to the Sakita/Miwa classification by EGD at screening can be re-enrolled if the subjects are confirmed healing and provide informed consent for the second time.)
13. Need for continuous concomitant therapy with:
- anticoagulants/antiplatelets (including aspirin <325 mg daily)
 - PPI (except for the investigational product)
 - H₂-receptor antagonists
 - M₁-receptor antagonists
 - Hp eradication therapy
 - Antacid
 - Prostaglandin analogue indicated for peptic ulcers (e.g. MISO)
 - Anticholinergics used for GI indications
 - Gastrointestinal promotility drugs
 - any drug known to have drug interactions with D961H and/or omeprazole, (e.g. human immunodeficiency virus (HIV) proteinase inhibitor such as atazanavir

sulphate and so on, diazepam, phenitoin, warfarin, tacrolimus hydrate, digoxin, methylidigoxin, itraconazole, gefitinib, voriconazole)

- Anticancer drugs
 - mucosal-protectants
14. Any significant “alarm symptoms” within 24 weeks prior to registration, such as, unintentional weight loss, gastrointestinal bleeding, jaundice, or other sign indicating severe or malignant disease.
 15. Subjects with disease/symptom allowing no administration of investigational product, such as known or suspected allergy or sensitivity to PPI.
 16. Any history of a generalised bleeding disorder resulting from haemorrhagic diathesis (e.g., abnormalities in clotting factors or platelets).
 17. Use of a PPI, or H₂-receptor antagonist within one week prior to registration.
 18. History of drug addiction or alcoholism within the past 12 months before registration.
 19. Inability to understand or provide informed consent.
 20. Inability or unwillingness to take investigational product according to dosing instructions.
 21. Inability to undergo EGD, or unwillingness to undergo multiple EGD.
 22. Involvement in the planning and conduct of the study (applies to both AstraZeneca staff or staff at the study site)

Rationale for exclusion criteria

Above criteria for excluding concomitant diseases, concomitant drugs, and specific patients' conditions are established since these factors may influence on the evaluation of the inhibitory effects of the investigational products and the safety of the patients.

3.3.4 Restrictions

Subjects must follow the following restrictions during the study period:

1. The subject must fast before blood sampling for biochemistry test and undergoing EGD according to the procedures specified by the study centre.
2. If the subject has been taking DMARD before registration, it must have been taken for four weeks or longer before registration at the constant dose. The dose is expected to be taken at the constant dose during the period from the registration to the day of the last scheduled visit or withdrawal.

3.3.5 Discontinuation of subjects from study treatment or assessment

3.3.5.1 Criteria for discontinuation

Subjects may be discontinued from study treatment and assessments at any time.

Specific reasons for discontinuing a subject from this study are:

- Voluntary discontinuation by the subject who is at any time free to discontinue his/her participation in the study, without prejudice to further treatment
- Safety reasons as judged as the patient to be discontinued by the investigator(s) and/or AstraZeneca K.K.
- Severe non-compliance to protocol as judged by the investigator(s) and/or AstraZeneca K.K.
- Incorrect enrolment i.e., the subject does not meet the required inclusion/exclusion criteria for the study
- Subject lost to follow-up
- Occurrence of an event in conflict of exclusion criteria (e.g., pregnancy)
- Development of gastric and/or duodenal ulcer
- Difficulty to conduct the study as judged by the investigator(s) due to the presence of gastric and/or duodenal mucosal lesion such as bleeding.
- Permanently stopping treatment with daily NSAID
- Others as judged appropriate by the investigator(s) (reasons for discontinuation must be recorded in eCRF)

3.3.5.2 Procedures for discontinuation

Subjects who discontinue should always be asked about the reason(s) for their discontinuation and the presence of any AEs. If possible, they should be seen and assessed by an investigator(s). AEs should be followed up. The subject should return a patient's diary and investigational products.

Should protocol led dosing be stopped during the study, the investigator(s) will perform the best possible observation(s), test(s) and evaluation(s) as well as give appropriate medication and all possible measures for the safety of the subject. In addition, they will record on the eCRF the date of withdrawal, the reasons, and so on. They will also immediately inform AstraZeneca K.K. of the withdrawal. Any SAE should be communicated to AstraZeneca K.K. according to the procedures defined in Section [4.7.1.3](#).

3.4 Treatments

3.4.1 Identity of test product and comparator

Formulation, content, and manufacturer of the investigational products are described in [Table 3](#).

Table 3 **Investigational products**

Investigational product	Formulation and content	Formulation number	Manufacturer
D961H capsule 20 mg	Enteric coated capsule containing D961H 22.3 mg with D961H pellets filled into a hard capsule	H 1189-04-01	AstraZeneca Sweden Operations Drug Product Supply

Packaging of the investigational product:

Fourteen capsules of D961H 20 mg will be packed in a blister pack under the responsibility of Investigational Products, AstraZeneca R&D Mölndal, Sweden. 30 blister packs (420 capsules in total) will be packed in a paper box.

3.4.2 Doses and treatment regimens

One capsule of the investigational product will be orally given once daily after breakfast for the period of 52 weeks. The investigator(s) must instruct the patients to take the investigational product regardless the time on the day of the first prescription and take the investigational product after examination on the days of EGD and biochemistry test conducted.

3.4.3 Labelling

Labels are affixed to the paper box. Each label will contain the description of name of the investigational product, study code, batch number, quantity, expiry date, storage condition, instruction, name of sponsor and address, 'for clinical study use'.

3.4.4 Storage

All investigational products must be kept in a secure place under appropriate storage conditions. Appropriate storage conditions are described on the investigational product label. They are also described in the document 'Procedures for drug storage'.

3.4.5 Accountability

AstraZeneca K.K. will provide the study documents 'Procedures for drug accountability' and 'Procedures for drug storage', which describe the specific requirements.

Investigational product will not be distributed to the study site until the contract is concluded between the study site and AstraZeneca K.K.. The investigational product provided to the study site must only be used for the purpose and the dosage as directed by the clinical study protocol.

The investigator(s) and/or the Investigational Product Storage Manager must instruct the subject to return unused investigational products and used blister packs. The investigator(s) and/or the Investigational Product Storage Manager must also confirm the number of capsules returned and recorded in the 'Investigational Product Log'. If there is any discrepancy in the number of capsules prescribed, administered, and returned, the investigator(s) or the study coordinator must confirm the reason with the patient and record it in the eCRF. The

Investigational Product Storage Manager and the monitor must confirm that all unprescribed and remaining investigational products are returned to AstraZeneca K.K..

The Investigational Product Storage Manager is responsible for managing the unused investigational products and remaining investigational products returned from the patients from distribution to the study site until the return to AstraZeneca K.K..

3.5 Method of assigning subjects to treatment groups

The investigator(s) will explain about the study to potential candidates, and obtain written informed consent. Prior to registration, the investigator(s) will judge eligibility of the subjects who provided informed consent. Only of the subjects who are confirmed having gastric and/or duodenal ulcer in active or healing stage according to the Sakita/Miwa classification by EGD at screening can be re-enrolled once the subjects are confirmed healing and provide informed consent for the second time. Registration should be done only once for the same subject. Enrolment code and registration code once given to the patient who withdrawn from the study should not be reused.

At the time of informed consent obtained, an enrolment code will be allocated to each subject at each study site to identify the subject. The enrolment code (E01XXYYY) is composed of 4 digits (01XX) of centre number and 3 digits (YYY) of consecutive number in order of registration to screening at each study site. For the subjects who are confirmed having gastric and/or duodenal ulcer by EGD at screening and re-enrolled after the subjects are confirmed healing and provide informed consent for the second time, the number added 500 to the previous consecutive number (YYY) will be allocated. For centre number(s), see Supplement A “Investigators and Study Administrative Structure”.

After confirming the eligibility of the subject who has given his/her consent, the investigator(s) will register the subject in accordance with the manual of procedure of subject registration provided by AstraZeneca K.K.

3.6 Blinding and procedures for unblinding the study (Not applicable)

3.7 Pre-study, concomitant and post-study treatment(s)

The use of all medications including investigational products and over-the-counter drugs during the study period must be recorded in the appropriate sections of the eCRF. However, drugs used for pre-treatment of EGD (e.g. xylocaine, anticholinergic agents, anti-anxiety agents) will not be recorded in the eCRF.

3.7.1 Allowed concomitant treatments

The following treatments can be used concomitantly during the study period.

- The treatment, which is considered necessary for the subject’s safety and well-being (also when deterioration of underlying disease such as osteoarthritis, rheumatoid arthritis, or lumbago is observed).

- Drugs used for pre-treatment of EGD (e.g. xylocaine, anticholinergic agents, anti-anxiety agents)

3.7.2 Allowed concomitant treatments with some limitations

The following treatments can be used concomitantly with some limitations.

- DMARD (However, if the subject has been taking DMARD before registration, it must have been taken for four weeks or longer before registration at the constant dose. The dose must be kept constant as much as possible during the period from the registration to the day of the last scheduled visit or withdrawal.)

3.7.3 Prohibited concomitant treatments

[Prohibited treatments prior to registration]

The following treatments cannot be used concomitantly for one week prior to registration.

- PPI
- H₂-receptor antagonists

[Prohibited concomitant treatments after registration]

The following treatments cannot be used concomitantly after registration:

- anticoagulants/antiplatelet drugs (doses of aspirin >324 mg daily are acceptable)
- PPI (except for investigational product)
- H₂-receptor antagonists
- M₁-receptor antagonists
- Hp eradication therapy
- antacid
- drugs classified as anticholinergics used for GI indications (scopolamine butylbromide used for pre-treatment before EGD is acceptable)
- gastrointestinal promotility drugs
- prostaglandin analogue indicated for peptic ulcer (e.g. MISO)
- any drug known to have drug interactions with D961H and/or omeprazole (e.g. HIV proteinase inhibitor such as atazanavir sulphate and so on, diazepam [use for pre-treatment before EGD is acceptable], phenitoin, warfarin, tacrolimus hydrate, digoxin, methylidigoxin, itoconazole, gefitinib, voriconazole)

- anticancer drugs
- mucosal-protectants

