- j All SAEs and AEs resulted in the subject’s withdrawal that occurred from the time when informed consent was obtained will be recorded in the eCRF. For AEs other than SAEs and AEs resulted in the subject’s withdrawal, only those occurring from initial administration to the last scheduled visit or withdrawal will be recorded in the eCRF.

- k If the subject discontinues the study before completing the treatment period (52 weeks), the subject should undergo the tests planned for Visit 15 (Week 52) as much as possible.
- l Only a haematology test should be conducted (See Section [4.7.2](#) for details.)
- m If these tests were missed at screening, they can be done at any visit until discontinuation/completion of the study.
- n Test data obtained before informed consent can be used with the consent of the subjects, if the test was conducted within 2 weeks prior to the registration.

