6.4.2.2 Severity of gastric mucosal lesion by modified LANZA score

Severity of gastric mucosal lesion will be evaluated using the modified LANZA score based on the results of EGD at pre-dose and at Weeks 4, 12, 24 and 52 after initial administration. Descriptive statistics of the modified LANZA score at each time point of measurement will be calculated. Descriptive statistics of the changes from baseline will also be calculated.

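### The baseline EGD may predate the one-week bar on PPIs and H₂-receptor antagonists, so change from baseline in modified LANZA score can be biased by an amount the protocol does not allow one to size

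*Protocol*

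**What the plan says.** **EGD window.** Inclusion criterion 2 (Protocol 3.3.2) requires an ulcer scar "confirmed by EGD findings obtained within two weeks prior to the registration". Note n to Table 2 (3.1), which is also attached to the mucosal lesion assessment, adds: "Test data obtained before informed consent can be used with the consent of the subjects, if the test was conducted within 2 weeks prior to" registration. Section 4.6.2.1 schedules LANZA scoring at screening and at Weeks 4, 12, 24 and 52, so the screening EGD is the only pre-dose one.

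**Drug window.** Exclusion criterion 17 (3.3.3) bars: "Use of a PPI, or H₂-receptor antagonist within one week prior to registration". Section 3.7.3 repeats this for the two classes: "The following treatments cannot be used concomitantly for one week prior to registration". Exclusion criterion 13 is broader in drugs but narrower in scope, as it applies to: "Need for continuous concomitant therapy with" the listed agents.

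**Analysis.** Section 6.4.2.2 summarises the LANZA score at each time point and adds: "Descriptive statistics of the changes from baseline will also be calculated". It does not distinguish subjects by recent acid suppression.

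**The concern.** Acid suppression is the mechanism under study. If a baseline EGD is done while a subject takes a PPI or H₂-receptor antagonist, or just afterwards, the score is not an untreated value. If those drugs lower the score, the baseline is too low, and the later change on D961H shows too little improvement or even apparent worsening.

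The study has one arm and no comparator, so change from baseline is the only within-study contrast for this variable. The results go into an approval application (6.6). If the date of last use is not collected, no later analysis can separate affected baselines from unaffected ones.

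**Working it through.** There is no planned figure to reproduce. The check is day arithmetic, followed by an illustration.

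**1. Windows, with registration as day 0.**
- EGD permitted: day -14 to day 0, which is 15 days (3.3.2; Table 2, note n).
- PPI and H₂-receptor antagonist use barred: day -7 to day 0 (exclusion 17; 3.7.3). The last permitted day of use is day -8.
- Overlap of a permitted EGD with permitted use: day -14 to day -8, which is 7 days. As a share this is 7/15 = 47%, or 7/14 = 50% if day 0 is left out.

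**2. Carry-over beyond the overlap.** With a last dose on day -8, an EGD on day -7 follows it by 1 day and an EGD on day -3 by 5 days. The calendar overlap therefore does not describe everyone with a recently treated baseline.

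**3. Does anything else close the gap?**
- Exclusion 13 removes subjects with a continuing need for these drugs. It does not remove those who used them and stopped by day -8.
- No second pre-dose EGD is scheduled.
- Section 3.7 requires medication to be recorded during the study period. Exclusion 7 describes that period as starting on the day of consent. Visit 1 collects concomitant drugs (4.2), but no text asks for the last dose date relative to an EGD done before consent.

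**4. Is such use plausible?** Section 1.2 reports a guideline recommending PPIs and high-dose H₂-receptor antagonists, among other options, for high-risk NSAID users, which is the population enrolled. Exclusion 12 and section 3.5 also allow subjects with an ulcer at screening to re-enrol once it has healed. Both suggest that some use is likely, but neither gives a proportion.

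**5. Illustration only.** Let f be the share of subjects with an affected baseline and d the lowering of their score. The shift in mean change is f × d. Neither value is in the protocol, so all of these are assumptions:

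| f | d = 0.5 | d = 1.0 | d = 1.5 |
|---|---|---|---|
| 10% | 0.05 | 0.10 | 0.15 |
| 30% | 0.15 | 0.30 | 0.45 |
| 50% | 0.25 | 0.50 | 0.75 |

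For example, with f = 30% and d = 1.0, a true mean change of -1.0 would be observed as -1.0 + 0.30 = -0.70.

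**6. Effect of aligning the windows.** If the two windows had the same length, the overlap would fall from 7 days to 0. An EGD on the first permitted day could still follow the last dose by 1 day, because the drug-free interval is counted from registration and not from the EGD.

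**The case against.** **Different purposes.** One rule sets how recent the eligibility EGD must be and the other sets a drug-free interval before registration. The protocol never says that they should coincide. This stands: the two rules do not formally contradict each other. They are nevertheless combined in one analysis that treats the EGD as an untreated starting point.

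**Limited exposure and weight.** Exclusion 13 removes continuing users. LANZA is one of three secondary efficacy variables, no hypothesis is tested (6.1), and efficacy against placebo is assessed in a separate study (1.2). Scores at each visit are also reported, and the post-dose values do not depend on baseline. The likely error runs against the drug. All of this stands and keeps the point modest.

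**Left to the SAP.** A subset table can be specified there. The date of last use before an EGD done ahead of consent cannot be recovered there unless the eCRF collects it.

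**Stronger readings that a reader might infer.**
- *That the change from baseline is biased.* The protocol supports only that it can be.
- *That about half of subjects are affected.* The 7 of 14 or 15 counts calendar days, not subjects.
- *That ulcers at Week 4 should be split by prior use.* Taking the overseas rate of 5.2% over 6 months from Table 1, 130 × 0.052 = 6.8 ulcers. At a constant rate about 6.8 × 4/26 = 1.0 would fall by Week 4, too few to divide. Any pre-dose EGD also leaves some gap before the first dose.
- *That the LANZA and symptom baselines conflict.* Symptoms cover the 7 days before Visit 2, which matches the drug bar, and the two variables are never combined.

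**Conclusion.** The point holds as a limited one. As written, the protocol accepts a baseline LANZA score obtained on, or shortly after, a PPI or H₂-receptor antagonist, and no other provision prevents or flags it. Change from baseline in 6.4.2.2 can therefore be biased. The direction is probably toward understating improvement, on the assumption that acid suppression lowers the score. The size is unknown, since the share of subjects affected and the effect on the score are not given, and the f × d values are illustrative only. The safety objective and the symptom baseline are not affected. A correction is worth making because it is cheap and the missing date may not be recoverable later.

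**What to change.** 1. The sponsor should reconcile the EGD window in 3.3.2 and Table 2 with the drug window in 3.3.3 (exclusion 17) and 3.7.3, and state how each relates to the EGD date. Which window should change is for the sponsor to decide.
2. Record in the eCRF the date of last PPI or H₂-receptor antagonist use relative to the baseline EGD, including EGDs done before consent.
3. In 6.4.2.2, present LANZA change from baseline for all subjects and, beside it, for subjects whose baseline EGD was not done on or shortly after such use. Define the interval that counts as shortly after before database lock.

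The cost is one eCRF date and one extra table. The second summary will rest on a smaller subset and will be less precise. Recording the date and adding the table require no change to visits or sample size.
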